1.0 INTRODUCTION

1.1 Study Design

This is a non-randomized pilot study to assess the objective response rate and durability of response of combination Trans-Arterial Chemoembolization (TACE) with immediate stereotactic body radiation therapy (SBRT) in the treatment of unresectable hepatocellular carcinoma (HCC). Eligible patients will be selected based on having a lesion greater than 3 cm which would make them ineligible for other local therapies such as TACE and thermal ablation (TA). Eligible, consented, and registered patients will be treated with two sessions of standard TACE with ethiodol separated by a 4-week interval. After ensuring adequate return to baseline liver function, the patients will then be treated with SBRT to the targeted lesion to 30-40 Gy in 5 fractions. Tumor response will be assessed using mRECIST criteria as well diffusion weight imaging (DWI) via Magnetic Resonance Imaging (MRI) surveillance. In addition, tolerability and toxicity will be recorded via CTCAE v. 5.0. The essential hypothesis of this study is that combination TACE and SBRT for > 3 cm HCC will produce higher response rates and durable control compared to historical controls of TACE alone.

1.2 Primary Objectives

1.2.1 To determine the objective response rate up to 1 year in patients with HCC treated with combination TACE and SBRT.

1.3 Secondary Objectives

1.3.1 To determine the time to progression (TTP) of the treated lesion.

1.3.2 To determine the overall survival (OS) of patients as defined from completion of treatment until death.

1.3.3 To determine the progression free survival (PFS) of patients as defined from the completion of treatment until disease progression in the treated lesion, liver, or distant metastases.

1.3.4 To determine the tolerability and toxicity of combination TACE and SBRT in this population.

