4.0 DELIVERY OF TACE

4.1 Initial TACE will be delivered per standard protocol

4.2 After 3 to 8 weeks following the intial TACE, patients will return for labwork and consideration for a second TACE to the same site. TACE will not be repeated if the bilirubin is > 3 ng/mL.

4.3 Prior to preceding to radiation therapy, the patient will have labwork done including CBC and LFTs to assess return to within grade 2 elevations of baseline labwork prior to proceeding onto radiation.

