5.6 Timing of Radiation

5.6.1 The first radiation treatment should begin within 7 days of the second TACE. Acceptable variation would be within 21 days of completion of TACE.

5.6.2 Per protocol, all external beam radiation treatments should be delivered within 15 calendar days. An acceptable variation is 16-21 calendar days. Treatment requiring greater than 22 calendar days constitutes a major protocol variation.

5.7 PTV coverage: The intent is for the prescription dose to cover 95% of the PTV. The PTV should be treated to as high a dose as possible, respecting normal tissue constraints, as a dose response has been observed. Modifying a PTV due to close proximity of adjacent OARs is not permitted. An acceptable variation per protocol would be 90-95% PTV coverage.

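### OS and PFS start only when all treatment is complete, PFS leaves out death, TTP has no start date, and the analysis set for the primary response rate is not defined

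*Combined protocol and SAP*

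**What the plan says.** Section 1.3.2: "To determine the overall survival (OS) of patients as defined from completion of treatment until death". Section 1.3.3 defines PFS "as defined from the completion of treatment until disease progression in the treated lesion, liver, or distant metastases"; death is not listed as an event. Section 1.3.1 reads "To determine the time to progression (TTP) of the treated lesion" and gives no start date. Section 8.2 names the three endpoints for medians and Kaplan-Meier curves. It adds no origin, event, censoring rule or analysis set.

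Section 8.1 describes study treatment as TACE, a second TACE, then five radiation fractions. Appendix D places time 0 at TACE #1.

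The protocol foresees patients who do not finish:
- Section 4.2: "TACE will not be repeated if the bilirubin is" above a stated level.
- Section 4.3 requires laboratory work "to assess return to within grade 2 elevations of baseline labwork prior to proceeding onto radiation".
- Sections 5.9 and 5.9.1 allow radiation to be discontinued.
- Section 6.7 keeps patients who had TACE but no SBRT in follow-up. It gives them no start date and no role in the analysis.

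For the primary endpoint, Section 1.2.1 speaks of response "in patients with HCC treated with combination TACE and SBRT". Section 8.2 applies a one-sample binomial test in patients, without further qualification. Section 8.1 takes its 82% power from a target of 40 enrolled. It also reports that the 30th patient had been enrolled and that primary analyses were under way.

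**The concern.** A clock that starts at the end of a multi-step regimen counts only patients who lived to reach that point. A death during TACE or SBRT falls before time zero, and a patient who stops early has no completion date unless completion means the end of whatever treatment was received. The plan does not say which. Because PFS omits death, a patient who dies without documented progression is not an event from any origin. With no stated origin, TTP can be computed in more than one way.

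The response rate has a parallel gap with more at stake, because it carries the only planned test. The wording of Section 1.2.1 does not define a completer set, but it allows one. While the set is open, it could be settled with results in view.

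**Working it through.** **Time before the clock starts.** Inputs: 3 to 8 weeks from TACE #1 to TACE #2 (Section 4.2, Appendix D); 1 to 3 weeks from TACE #2 to SBRT (Appendix D). Five fractions every other day (Sections 5.1.2 and 8.1) fall on days 1, 3, 5, 7 and 9, so about 9 days. For the longest course, Section 5.6.2 says "An acceptable variation is 16-21 calendar days".

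- Shortest by Appendix D: 21 + 7 + 9 = 37 days (5.3 weeks).
- Section 5.6.1 says "The first radiation treatment should begin within 7 days of the second TACE". If SBRT followed at once: 21 + 0 + 9 = 30 days (4.3 weeks).
- Longest acceptable: 56 + 21 + 21 = 98 days (14.0 weeks).

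**Possible effect on a one-year rate.** Assume 2 of 40 patients die before SBRT ends and 8 others have an event by one year. Counting the early deaths gives 30/40 = 75.0%; omitting them gives 30/38 = 78.9%. With 4 early deaths the figures are 28/40 = 70.0% and 28/36 = 77.8%. These counts are assumptions, and the shift of the one-year mark is ignored.

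**The plan's power.** Two-sided exact test, null ORR 0.52, alternative 0.75, equal tails. The cut-off c is the smallest value with P(X ≥ c | n, 0.52) ≤ 0.025. For n = 40, c = 28, the upper tail is 0.0160 and power is P(X ≥ 28 | 40, 0.75) = 0.821. The stated 82% reproduces.

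**One data set, two denominators.** Assume 4 of 40 do not complete and there are 26 responders, all completers.
- Completers: 26/36 = 72%; P(X ≥ 26 | 36, 0.52) = 0.0109. The cut-off at n = 36 is 26, so the test succeeds.
- All patients: 26/40 = 65%; P(X ≥ 26 | 40, 0.52) = 0.0676. The cut-off is 28, so the test fails.

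**Error rates and power.** Let k be the number of non-completers and r their ORR.
- For false positives, hold the all-patient ORR at 52%, so the completer ORR is (20.8 − k·r)/(40 − k).
- For all-40 power and for discordance (completer test positive, all-40 test negative), set completers at 75% and add Bin(40 − k, 0.75) to Bin(k, r).

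Each cell gives r = 0 / 0.25 / 0.52:

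| k | Completer-only false positives | Discordance | All-40 power |
|---|---|---|---|
| 2 | 3.0 / 2.1 / 1.3% | 12 / 7 / 3% | 66 / 71 / 77% |
| 4 | 5.4 / 2.6 / 1.1% | 29 / 15 / 5% | 44 / 58 / 72% |
| 6 | 17 / 7.1 / 2.2% | 57 / 35 / 14% | 22 / 44 / 66% |

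The all-40 test stays at 0.7 to 1.6% false positives throughout. Completer-only power at 75% is 78%, 73% and 79% for k = 2, 4 and 6. The plan does not say which exact test it uses. The minimum-likelihood version changes only the k = 4 row: the cut-off at n = 36 becomes 25, false positives become 10.5 / 5.6 / 2.6%, discordance 40 / 25 / 12%, and completer-only power 83%. Under that version 26/36 still succeeds and 26/40 still fails.

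**The case against.** OS, PFS and TTP are descriptive endpoints in a single-arm pilot, and no test depends on them. Timing from the end of SBRT is partly a design choice, since Section 7.2 and Appendix D schedule the MRIs from there. Eligibility (ECOG 0, Child-Pugh A or B7 without ascites, one lesion up to 7 cm, no vascular invasion or metastases) gives no reason to expect many early deaths. All of this stands, and it limits the size of the time-to-event problem. It does not supply a start date for patients who never finish, or make death a PFS event.

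On the response rate, a patient without SBRT has still had TACE, and the only TACE response rate in the plan is 52.5%. If non-completers respond at about 52%, completer-only false positives stay at about 1 to 2% with equal tails (2.6% for 4 lost with the minimum-likelihood test). The 5.4% and 17% figures need no responses at all among non-completers. This too stands.

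A reader might infer that the plan restricts the primary analysis to completers and so inflates the response rate. The documents do not support that. Section 1.2.1 permits such a set without defining it, no passage ties laboratory recovery to imaging response, and the denominator behind the 52.5% benchmark is not given. A reader might also infer that 82% power holds only if all 40 are in the denominator. It does not: a completer set of 39 has 84.6% power (cut-off 27), and all-40 power falls below 82% if non-completers respond less often. What the 82% requires is 40 patients in the set and a 75% ORR across all of them.

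**Conclusion.** The definitions need correction. Followed literally, Sections 1.3.2 and 1.3.3 leave out deaths in the roughly 4 to 14 weeks before SBRT ends, give patients who do not finish no clear start, and never count death in PFS; Section 1.3.1 gives TTP no origin. The effect is on medians and curves.

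The undefined ORR set matters more, because it can turn the primary result from success to failure, as 26/36 against 26/40 shows. How likely that is cannot be settled from the documents: every non-completion count and non-completer response rate above is assumed. The direction of any bias is also unknown, and if non-completers respond like the rest there is no inflation. The plan's 82% is correct under its own assumptions.

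**What to change.** - **Sections 1.3.1 to 1.3.3:** start OS, PFS and TTP at TACE #1 (Appendix D time 0). Count death from any cause as a PFS event. Censor TTP at death without progression, or treat death as a competing risk. Report times from SBRT completion beside these as a labelled landmark analysis for completers.
- **Sections 1.2.1 and 8.2:** make the primary ORR set all patients who start TACE #1, scored from their planned MRIs. Count patients with no post-baseline MRI as non-responders. Report the completer ORR as a labelled sensitivity analysis. Disclose that the set was fixed after 30 patients were enrolled and analyses had begun.
- **Section 6.7:** state the date from which the MRI schedule runs for patients who do not finish SBRT, such as the last treatment received, because Section 7.2 counts from SBRT completion.
- **Section 8.1:** state that 82% power assumes 40 patients in that set and a 75% ORR across all of them. Enrolment precedes TACE #1, so 40 enrolled may not mean 40 in the set.
- **Sections 4.2 and 5.6.1:** the sponsor should reconcile whether SBRT follows when TACE #2 is withheld, since Section 5.6.1 dates SBRT from the second TACE.

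The cost is mainly text, using data largely already planned. Completers' times lengthen by about 4 to 14 weeks, with no scheduled response MRI in that period. Power falls below 82% if non-completers respond less often: 44 to 72% with 4 non-completers responding at 0 to 52% and completers at 75%. Fixing a primary analysis set this late carries its own risk of being shaped by results. Disclosure and the parallel completer result reduce that risk but do not remove it.

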5.8 Radiation Therapy Adverse Events

The criteria used for the grading of toxicities encountered in this study are Common Toxicity Criteria (CTC) version 4.0.

Very likely (80-90%)

- Fatigue (which generally goes away after the radiation therapy is completed)
- Skin irritation, redness, itchiness, discomfort
- Temporary changes in blood work (decrease in blood counts, increase in liver enzymes), without symptoms

Less likely (30%)

- Nausea, vomiting (during therapy) – more common if stomach or gastrointestinal track irradiated
- Gastric, esophagus, small bowel or large bowel irritation/ulceration, bleeding, fistula, obstruction or changes in motility following therapy (may require medications or surgery) (<10% permanent changes)
- Chest wall pain, rib fracture (< 10%)

Less likely, but serious (<20%)

- Radiation-induced liver disease (RILD) (<5%). Classic RILD is a clinical diagnosis of anicteric ascites, hepatomegaly and elevation of alkaline phosphatase relative to other transaminases that may occur 2 weeks to 3 months following radiation to the liver.
- Non-classic RILD includes elevation of liver enzymes and/or any decline in liver function within 12 weeks from start of therapy (~20%). RILD can lead to liver failure that could lead to death. There is an increased risk of liver toxicity in patients with large tumors and in patients with pre-existing liver disease.
- Permanent thrombocytopenia (<1%); this may lead to bleeding
- Kidney injury (<1%); this may lead to changes on imaging and more rarely the need for medication.

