6.7 If a patient received his/her TACE treatments and did not receive SBRT, he/she will nevertheless be followed by the same follow up schedule as above except for the OTVs and one month post-radiation visit.

6.8 Patients will be followed after one year per standard medical care.

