8.2 Data Analysis

Descriptive statistics (median, min-max, range, and percentages) will be provided for the pretreatment data such as demographics and comorbidities, and post-treatment complications. To assess the 1-year response rate in patients, one-sample binomial test will be conducted. For the secondary objectives,

descriptive analysis will be applied to determine the median survival times and Kaplan-Meier survival curves will be plotted for the endpoints:

- Time to progression
- Progression-free survival
- Overall survival

All analysis will be performed using SAS version 9.3 (SAS Institute Inc., Cary, NC, USA).

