Appendix B: mRECIST Assessment

Table 2 Assessment of Target Lesion Response: Conventional RECIST and mRECIST Assessment for HCC Following the AASLD-JNCI Guideline

[figure not shown]
RECIST	mRECIST for HCC
CR = Disappearance of all target lesions	CR = Disappearance of any intratumoral arterial enhancement in all target lesions
PR = At least a 30% decrease in the sum of diameters of target lesions, taking as reference the baseline sum of the diameters of target lesions	PR = At least a 30% decrease in the sum of diameters of viable (enhancement in the arterial phase) target lesions, taking as reference the baseline sum of the diameters of target lesions
SD = Any cases that do not qualify for either partial response or progressive disease	SD = Any cases that do not qualify for either partial response or progressive disease
PD = An increase of at least 20% in the sum of the diameters of target lesions, taking as reference the smallest sum of the diameters of target lesions recorded since treatment started	PD = An increase of at least 20% in the sum of the diameters of viable (enhancing) target lesions, taking as reference the smallest sum of the diameters of viable (enhancing) target lesions recorded since treatment started

AASLD, American Association for the Study of Liver Diseases; JNCI, Journal of the National Cancer Institute; HCC, hepatocellular carcinoma; mRECIST, modified Response Evaluation Criteria in Solid Tumors; CR, complete response; PR, partial response; SD, stable disease; PD, progressive disease.

Taken from Lencioni and Llovet. Modified RECIST (mRECIST) Assessment for Hepatocellular Carcinoma. 2010;30:52-60.

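### Section 1.3.3 ends PFS only at progression and section 8.2 adds no event or censoring rule, so read literally the endpoint is time to any progression labelled PFS

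*Combined protocol and SAP*

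**What the plan says.** Three time-to-event endpoints appear in section 1.3.

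- **TTP (1.3.1):** "To determine the time to progression (TTP) of the treated lesion". No starting point is given.
- **OS (1.3.2):** "overall survival (OS) of patients as defined from completion of treatment until death". Death is named.
- **PFS (1.3.3):** "as defined from the completion of treatment until disease progression in the treated lesion, liver, or distant metastases". Death is not named.

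Section 8.2 handles all three in one sentence: "descriptive analysis will be applied to determine the median survival times and Kaplan-Meier survival curves will be plotted for the endpoints". It does not say what counts as an event or when a patient is censored. Appendix B defines progression by tumor size alone: "PD = An increase of at least 20% in the sum of the diameters of viable (enhancing) target lesions". That table covers target-lesion response and would not be expected to mention death, so it neither causes nor closes the gap.

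On the time origin, 8.1 describes study treatment as two TACE sessions followed by radiation. Section 4.3 places a laboratory check before SBRT, to "assess return to within grade 2 elevations of baseline labwork prior to proceeding onto radiation", so some patients may stop after TACE. Section 6.7 keeps them under observation: "If a patient received his/her TACE treatments and did not receive SBRT, he/she will nevertheless be followed by the same follow up schedule". Appendix D labels TACE #1 as time zero, but only as a schedule marker.

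**The concern.** A reader of a PFS curve takes it to show progression or death, whichever comes first. Under 1.3.3 as worded, a patient who dies without progression has had no event. TTP and PFS would then differ only in the sites counted (treated lesion against any site), and no stated endpoint would combine progression with death.

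Such deaths are possible in this population. Section 5.8 says of radiation-induced liver disease: "RILD can lead to liver failure that could lead to death". A death of that kind would drop out of the PFS curve at the moment it became relevant. Section 1.1 frames the study as a comparison of durable control with historical controls, so a PFS figure that leaves out deaths could be set beside published figures that include them.

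A smaller question is where the clock starts for TTP, and for OS and PFS in patients who never reach SBRT. It bears on who is in each curve.

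**Working it through.** **1. The plan's own figure.** The only stated power is for the response rate in 8.1: N = 40, null 52%, alternative 75%, two-sided exact test at 0.05. The exact binomial test rejects upward at 28 or more responses of 40. The upper tail is 0.0160, the total two-sided level is 0.0388 (lower region 14 or fewer), and power is 0.8209. The stated 82% is reproduced. No PFS quantity enters it.

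**2. Direction, if deaths are censored on the date of death.** At each event time with n at risk, the Kaplan-Meier factor is 1 - (progressions + deaths)/n when deaths count and 1 - progressions/n when they are censored. The numbers at risk are the same, so the second factor is never smaller. The curve as written is therefore never below progression-or-death PFS. In simulation (40 patients, 1,500 runs in each of six assumed scenarios) no run fell below at any time.

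**3. Direction, if deaths are censored at the last MRI.** The plan does not exclude this. Take 10 patients. One has a last MRI at 6 months and dies at 8.9 months; another progresses at 7 months.

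- At 7 months, deaths counted: 9/10 = 0.900. Death censored at 6 months: 8/9 = 0.889, which is lower.
- After 8.9 months, deaths counted: 0.900 × 8/9 = 0.800. As written, still 0.889, which is higher.

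So the curve can dip briefly below.

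**4. Size at 12 months.** Inputs: N = 40 (target) or 30 (first cohort), both from 8.1. P is the number of progressions by 12 months, assumed at 20-40% because the documents give no rate. k is the number of deaths without progression. All patients are assumed followed to 12 months.

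- Progression-or-death PFS = (N - P - k)/N.
- As written, lowest value = (N - P - k)/(N - k), with all deaths censored before the first progression.
- As written, highest value = (N - P)/N, with all deaths censored after the last progression.

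The lowest value already assumes the earliest possible censoring and still exceeds (N - P - k)/N. The 12-month direction therefore holds under either censoring date.

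| N | P | k | Deaths counted | As written | Gap (points) |
|---|---|---|---|---|---|
| 40 | 8 | 1 | 31/40 = 77.5% | 31/39 = 79.5% to 32/40 = 80.0% | 2.0-2.5 |
| 40 | 12 | 1 | 27/40 = 67.5% | 27/39 = 69.2% to 28/40 = 70.0% | 1.7-2.5 |
| 40 | 16 | 1 | 23/40 = 57.5% | 23/39 = 59.0% to 24/40 = 60.0% | 1.5-2.5 |
| 30 | 6 | 1 | 23/30 = 76.7% | 23/29 = 79.3% to 24/30 = 80.0% | 2.6-3.3 |
| 30 | 12 | 1 | 17/30 = 56.7% | 17/29 = 58.6% to 18/30 = 60.0% | 2.0-3.3 |

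For scale only, since no source gives the count: four such deaths in 40 with P = 12 give 24/40 = 60.0% against 24/36 = 66.7% to 28/40 = 70.0%. With k = 0 the two definitions coincide.

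**5. Why the remedy needs a horizon.** Protocol MRI ends at about 12 months (6.5, 7.2, Appendix D), and later follow-up is standard care (6.8). As an extreme case, suppose 28 of 40 are progression-free, 27 are censored at the 12-month MRI and one dies at month 20, with no later imaging. The risk set at month 20 is one patient, and PFS falls from 70% to 0.70 × (1 - 1/1) = 0%.

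**The case against.** The strongest reply is that the endpoint is called progression-free survival, a name that ordinarily includes death, and that 1.3.3 may be shorthand listing only the progression sites. That stands as a statement about intent. It does not settle the text: the plan gives its own definition, the OS line just above names death, and 8.2 adds no correction. Two analysts could draw two different curves from the same plan.

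Deaths without progression may also be few. Eligibility is ECOG 0 and Child-Pugh A or B7 without ascites. Section 5.8 puts classic radiation-induced liver disease below 5%, and the SBRT series in section 2.0 for which it is reported saw none. This limits the likely size but does not remove the omission.

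A reader might infer three stronger things that the documents do not support.

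- *That the PFS curve can only read at or above true PFS throughout.* This requires censoring on the date of death, and no section says which date applies.
- *That deaths were in fact censored, or that submitted figures are wrong.* Section 8.1 says that primary analyses were under way and a manuscript was anticipated. It does not show that PFS had been analysed, or how.
- *That the time-origin gap biases the results in a known direction.* For patients with no SBRT, completion of treatment could be read as the last treatment received. What is missing is the operational detail, not the concept.

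**Conclusion.** The PFS definition is wrong as written and should be corrected. The consequence is limited to a secondary, descriptive endpoint. Confidence is high on the textual omission. The 1.5-2.5 points per death (N = 40) rest on an assumed 20-40% progression and complete 12-month follow-up, and the total effect depends on a number of deaths that the documents do not give. The primary test is untouched, and deaths are not lost to the study, since OS and toxicity still record them. The origin question is a minor clarification with no fixed direction of effect.

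**What to change.** **PFS definition.** In 1.3.3 and again in 8.2, define PFS as time from the stated origin to first progression (treated lesion, liver or distant) or death from any cause. Censor patients who are alive and progression-free at their last disease assessment.

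**Late deaths.** State a rule for deaths after protocol imaging ends. One option is to report PFS up to the 12-month assessment window with numbers at risk, and to censor at the last assessment when death follows a long gap without imaging. Fix the length of that gap in advance and report how many deaths it affects.

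**Transparency.** Make the change by a dated amendment with IRB approval (9.1) and disclose that analyses of the first 30 patients had begun (8.1). Report the progression-only curve alongside, labelled time to any progression. Section 8.1 foresees further analyses after the first publication, so the correction is still useful.

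**Minor clarification.** State the origin for TTP, and for OS and PFS in patients who had TACE but no SBRT, and report how many of them are in each curve. The choice is a matter of judgement. TACE #1 is available to every treated patient, but Appendix D schedules no MRI between it and the first scan after SBRT, so early progression would be dated late.

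**Cost.** Wording in two sections, one amendment and a re-run of the curves. No new measurement is needed, because the date of death is already required for OS. The downside is that PFS may read somewhat lower.
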